The score for each category will be the single response within the category with the highest score (greatest difficulty). For example, in the "Eating" category, there are two answers (one for each item). If "Cut your food with a knife or fork" is marked as "3" and "Lift a full cup or glass to your mouth" is marked as "0", then the score for the "Eating" category would be "3" (the response indicating the greatest difficulty within the category). If a component question is left blank or the response is too ambiguous to assign a score, then the score for that category will be determined by the remaining completed question(s). However, if **any** "aids or devices" and/or "help from another person" items at the bottom of each page are checked, the category to which they apply will be adjusted upward to "2". If the basic score is **already** "2" or "3", the score remains unchanged. "Aids or devices" and "help from another person" can **only** change a category's score to "2"; they do **not** change the score to a "1" or a "3".

The score for the disability index will be the mean of the eight category scores. If more than two of the categories, or 25%, are missing, scale will not be scored. Otherwise, divide the sum of the categories by the number of answered categories. The higher score indicates greater disability.

HAQ-DI response

The HAQ-DI response is defined by an improvement of at least 0.3 score points compared to baseline.

Joint/bone structural damage

The primary score for analyses will be van der Heijde modified Total Sharpe score (vdH-mTSS) (van der Heijde 1999), The erosion score and joint space narrowing score will be analyzed in similar fashion.

Erosions will be assessed each hand (20 locations per hand) and each foot (6 locations per foot). The maximum erosion score is 200 for all 40 hand locations, and 120 for all 12 feet locations. Thus, the total possible erosion score is 320.

Joint space narrowing (JSN) will be assessed in each hand (20 locations per hand) and foot (6 locations per foot). The maximum score is 160 for all 40 hand joints, and 48 for all 12 feet joints. Thus, the total possible JSN score is 208.

Pencil-in-cup: Osteolysis of the proximal phalanx and the base of the distal phalanx resulting in a pencil like proximal phalanx covered by cup like base of the distal phalanx. Pencil-in-cup will be scored as “P” where applicable.

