Gross Osteolysis: Osteolysis of the phalanx resulting in a loss of the normal joint structure, usually accompanied by shortening of the length of the phalanx. Gross osteolysis will be scored as “G” where applicable.

If a joint or bone is not visible (e.g. poor film quality, missing imaging, severe misalignment, flexion deformity, dislocation) at the timepoint, the individual joint or bone will be coded as Not Visible (N).

If radiographs at the timepoint show a joint or bone with surgical fusion, replacement (prosthesis), or amputation, then the joint or bone will be scored Surgically Modified (S).

To obtain the total vdH-S score, scores for erosions and JSN in both the hands and feet will be added together. Any “P” or “G” will be considered the maximal score for the feature (erosions and JSN) per location in the calculation of the total vdH-S score. Any “N” or “S” will be considered null in the calculation of the total vdH-S score. The range of scores is 0 ~ 528.

The joints are divided into 10 segments according to [Table 12-1](#). In each segment an adequacy threshold is defined. For each segment, when the change from baseline values are available for at least the threshold number of joints, the change from baseline will be calculated for the segment, with missing joints imputed by the within-segment mean change over individual joints. Otherwise (i.e. if less than threshold number of joints have available change from baseline values), the segment change from baseline will be missing. When ≥ 6 segments have

[figure not shown]
evaluable change from baseline values, the overall change from baseline value will be calculated, with missing segments imputed by the mean change over segments. Otherwise (i.e. if ≤ 5 segments have evaluable change from baseline values), the overall change from baseline value will be missing.

[figure not shown]
[figure not shown]
Table 12-1 Segmental distribution

Segment	Total number of joints	Adequacy threshold	Joints at one side
PIP erosions	8	5	PIP2, PIP3, PIP4, PIP5
DIP erosions	8	5	DIP2, DIP3, DIP4, DIP5
MCP + thumb erosions	12	7	MCP1, MCP2, MCP3, MCP4, MCP5, INTERPHALANGEAL JOINT OF THE HAND
Wrist erosions	12	7	FIRST METACARPAL BONE, DISTAL RADIUS, DISTAL ULNA, TRAPEZOID-TRAPEZIUM, NAVICULAR BONE, LUNATE BONE
Foot erosions	12	7	MTP1, MTP2, MTP3, MTP4, MTP5, INTERPHALANGEAL JOINT 1
PIP JSN	8	5	PIP2, PIP3, PIP4, PIP5
DIP JSN	8	5	DIP2, DIP3, DIP4, DIP5

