For continuous variables, the change from baseline (of core) when available, will be summarized.

[REDACTED]

Figures will be provided for the following parameters:

- [REDACTED]
- DAS28-CRP and SF-36 PCS change from baseline.
- HAQ-DI score (change from baseline) overall and following the up-titration
- HAQ-DI response overall and following the up-titration
- HAQ-DI response by TNF- α inhibitor status.
- Remission response and low disease activity response according to DAS28-CRP
- [REDACTED].
- [REDACTED]

Individual listings will be considered for all efficacy variables of the study.

Joint/bone structural damage at Week 156, 208

The changes in joint/bone structural damage (total sharp score, and its components, erosion score and joint spacing narrowing score) will be summarized by the same treatment groups as follows using evaluable data of each x-ray reading session:

- Baseline to:
 - Week 24
 - Week 52
 - Week 104
 - Week 156
 - Week 208
- Week 24 to:
 - Week 52
 - Week 104
 - Week 156

[figure not shown]
- Week 208
- Week 52 to:
 - Week 104
 - Week 156
 - Week 208
- Week 104 to:
 - Week 156
 - Week 208

[figure not shown]
[figure not shown]
The above analyses will be done on both FAS and X-ray completers where X-ray completers are those subjects that had X-ray measures at baseline, Week 16/24, Week 52, Week 104, Week 156 and Week 208. Subgroup analyses by TNF-alpha inhibitor status will be provided.

Analyses will be performed for each reading campaign, as appropriate depending on the available data.

For the purpose of the campaign 3 the readings of baseline, week 156 and week 208 will be used for the analysis. Any data on week 260 will be shown only in listings.

Individual listings will be provided for Joint structural damage components.

13 Pharmacokinetic evaluations (change / add PD, PK/PD, Biomarkers, as needed)

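### Do the radiographic adequacy thresholds in SAP Table 12-1 need changing because one lost film fails every segment of that region?

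*SAP*

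**What the plan says.** SAP section 12.1 (Joint/bone structural damage) and Table 12-1 define five erosion segments and five joint space narrowing (JSN) segments. For each feature four segments are in the hands and one is in the feet. The table lists the joints of one side, and the segment total is twice that list. The PIP and DIP segments have 8 joints and a threshold of 5; the MCP plus thumb, wrist and foot segments have 12 joints and a threshold of 7.

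At or above the threshold, the segment change is calculated "with missing joints imputed by the within-segment mean change over individual joints". Below it: "Otherwise (i.e. if less than threshold number of joints have available change from baseline values), the segment change from baseline will be missing". Given six or more segments with "evaluable change from baseline values, the overall change from baseline value will be calculated, with missing segments imputed by the mean change over segments". If five or fewer "segments have evaluable change from baseline values), the overall change from baseline value will be missing".

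The SAP provides a code for unreadable sites: "If a joint or bone is not visible (e.g. poor film quality, missing imaging, severe misalignment, flexion deformity, dislocation) at the timepoint". Pencil-in-cup and gross osteolysis "will be considered the maximal score for the feature (erosions and JSN) per location in the calculation of the total vdH-S score". On the two components it says: "The erosion score and joint space narrowing score will be analyzed in similar fashion".

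Protocol section 6.4.2 has each hand/wrist and each foot radiographed separately, and provides for quality control and repeat films. SAP section 12.4 summarises change descriptively by reading session: "For the purpose of the campaign 3 the readings of baseline, week 156 and week 208 will be used for the analysis". It also provides individual listings of the structural damage components.

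**The concern.** Every threshold is one joint above half of a two-sided segment, and a film covers one side. A single lost film, at baseline or at the visit, therefore fails every segment of its region, and readings from the intact side go unused.

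- **One foot film lost.** The total change is still computed, but the feet are represented by the average hand segment. A joint in the filmed foot that goes from 0 to gross osteolysis contributes none of its 14 points (10 erosion + 4 JSN).
- **One hand film lost.** There is no total, although most sites were read. The same rule can accept a total from far fewer sites if they are spread differently.
- **Components.** Erosion and JSN have five segments each, so a six-segment minimum taken literally could never be met.

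At stake would be individual total changes, the number of patients with a value at Weeks 156 and 208, and possibly the mean change.

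**Working it through.** **Reproducing the plan's range.** SAP 12.1 gives 40 hand and 12 foot locations per feature.
- Erosion: 40 × 5 + 12 × 10 = 200 + 120 = 320.
- JSN: 40 × 4 + 12 × 4 = 160 + 48 = 208.
- Total: 320 + 208 = 528, as the SAP states, over 52 + 52 = 104 sites (80 hand, 24 foot).

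Protocol 6.4.2 gives maxima of 360 for erosion and 168 for JSN. These equal the hand total (200 + 160) and the foot total (120 + 48), so this looks like a labelling slip. It has no bearing on the thresholds.

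**Segments that pass after one lost film** (Table 12-1)

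| Film lost | Sites read | Segments passing | Total change |
|---|---|---|---|
| One foot | 80 + 12 = 92 | 8 (foot segments 6 of 12 < 7) | computed from 80 sites |
| One hand | 40 + 24 = 64 | 2 (hand segments 4 of 8 < 5, 6 of 12 < 7) | missing (2 < 6) |

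The smallest accepted set is four 8-joint and two 12-joint segments at threshold: 4 × 5 + 2 × 7 = 34 of 104 sites. The mechanism is as described.

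**Size of the foot-film error.** Both foot segments take the mean of eight hand segments, so the total is hand change × (1 + 2/8) = 1.25 × hand change. If the feet carry share f of the change, the relative error in that patient's expected total is 1.25(1 − f) − 1:
- f = 10%: +12.5%
- f = 20%: 0
- f = 40%: −25%

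The documents do not give f or the rate of lost films. Assuming 10% of patients are affected, the group mean moves by 0.10 × 12.5% = +1.25% to 0.10 × (−25%) = −2.5%. At 2% affected the range is +0.25% to −0.5%.

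**Size of the hand-film loss.** Assumed rates of 2%, 5% and 10% of the 460 enrolled give 9, 23 and 46 patients without a total. These are ceilings for those rates: only patients filmed at Weeks 156 and 208 count, and the protocol's Amendment 1 rationale already has 432 under treatment in September 2015.

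**The alternative: thresholds at half (4 of 8, 6 of 12).** All ten segments then pass after one lost film. The expected error is zero if which side is lost is unrelated to its change. The smallest accepted set falls to 4 × 4 + 2 × 6 = 28 sites.

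For individual error after a lost foot film, assume a mean total change of 2 points, Poisson counts, and a patient factor with mean 1 and coefficient of variation CV. The mean squared errors are:
- Current rule: 0.0625 × 2(1 − f) + 2f + [0.5(1 − f) − 2f]²(1 + CV²).
- Half threshold, two feet alike: 2f.
- Half threshold, only one foot progresses: 2f + 4f²(1 + CV²).

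Root mean squared errors:

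| f, CV | Current | Half, feet alike | Half, one foot only |
|---|---|---|---|
| 20%, 0 | √0.50 = 0.71 | √0.40 = 0.63 | √0.56 = 0.75 |
| 40%, 2 | √2.125 = 1.46 | √0.80 = 0.89 | √4.00 = 2.00 |
| 10%, 2 | √0.625 = 0.79 | √0.20 = 0.45 | √0.40 = 0.63 |

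The ranking depends on left-right symmetry and foot share, and the documents give neither.

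**Components.** The overall rule asks for 6 of 10 segments, which is 60%. The same proportion of five is 3 of 5. After a lost foot film each component has 4 of 5 and is computed; after a lost hand film each has 1 of 5 and is missing. Both outcomes agree with the total.

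**The case for a change.** The best argument for acting is that the behaviour is deterministic and cheap to address. A patient with progression only in the filmed foot is given a total change of 0. A patient with 64 of 104 sites read (62%) gets no total, while one with 34 (33%) can. For tender and swollen joint counts the same SAP scales up whatever was assessed, with no threshold. X-ray completers are defined by having X-ray measures, so a completer can lack a total. A half-threshold sensitivity derivation would need only stored joint scores, and it removes the average bias whatever the foot share. In simulated scenarios where the two feet were uncorrelated or positively correlated, it also had the lower root mean squared error throughout.

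The arithmetic stands, and so does the absence of average bias. The advantage in individual error does not hold generally: it reverses in two of the three one-foot rows above, and individual totals are where the effect mainly lies. Lowering the threshold also admits totals from even fewer sites, which widens the inconsistency complained of. Damage in the filmed foot is not hidden, because the component listings in SAP 12.4 can show it. Counts of filled segments and missing totals would be informative, but would change no result.

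**Conclusion.** No change to the plan. The thresholds do behave as described: a lost foot film means 80 of the 92 sites read are used, and a lost hand film leaves 2 of 10 segments and no total. Declining to extrapolate unless more than half of a segment is read is nevertheless a defensible rule, and withholding a total when half of all hand readings are gone is conservative rather than wrong.

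Radiographic change is not among the visible objectives, no formal hypothesis is tested, and the summaries are descriptive. The foot-film effect on a group mean stays within +1.25% to −2.5%, assuming 10% of patients lose a foot film and the feet carry 10% to 40% of the change. The repeat-film provision should help keep losses down, but the documents give no rate. Thresholds at half exchange one set of errors for another, and the documents do not show which is smaller in this population.

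The unstated component minimum is a gap that analysts would fill sensibly: handling the components like the total leads to 3 of 5. This rests on the visible text; the SAP also cites an efficacy analysis plan that is not among the documents and may state it.

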6.4.2 Radiographic assessments

Separate radiographs of each hand/wrist (PA) and each foot (AP) will be taken at Week 156, 208 and 260.

From time of implementation of Amendment 2, radiographs at Week 260 will not be obtained as part of the study.

Bone erosion, joint space narrowing (JSN), and total radiographic scores will be determined using a PsA modified van der Heijde-Sharp (vdH-S) scoring method ([van der Heijde 2005](#)) that includes the second through fifth distal interphalangeal (DIP) joints of each hand. Erosions (0–5 in the hands and 0–10 in the feet) and JSN (0–4) will be graded separately in six wrist joints, all metacarpophalangeal, proximal interphalangeal, and DIP joints of each hand, and the first interphalangeal joint and all metatarsal phalangeal joints for each foot. The total radiographic score (hands and feet combined) ranges from 0 to 528, with higher scores indicating more articular damage. The maximum total erosion score is 360. The maximum total JSN score is 168.

[figure not shown]
[REDACTED] Radiologists will be trained on the X-ray acquisition and further details will be provided in a manual for the radiologists, e.g. joint placement and beam positioning.

In case of analogue X-rays films, the original film will be sent to the central reading CRO and will undergo quality control and will be digitized. Standard film and cassettes will be provided to all centers that do not produce digital X-rays. In case of digital equipment, sites need to confirm minimum requirements with the imaging CROs. Digital X-rays will be transferred electronically.

In case of insufficient quality, the center will be advised and trained on any quality issues prior to the repeat X-ray and to keep any repeat X-rays to a minimum.

[figure not shown]
[figure not shown]
[figure not shown]
Subjects who discontinue study treatment before the end of the trial, hands/wrists and feet X-rays will be taken at the time of study treatment discontinuation. However, if a radiograph of hands/wrist and feet was performed within last 6 months of early discontinuation visit then it does not need to be performed. Likewise, if a scheduled X-ray at Week 156, 208 or 260 is scheduled less than 6 months after any prior hands/wrists and feet X-rays, it does not need to be performed. All following X-rays will be performed as scheduled.

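### The SAP fills a missing radiographic segment with the plain mean of the other segments, although segment maxima run from 32 to 120; scale the fill-in by joint count and set a separate minimum for the erosion and JSN scores

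*SAP*

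**What the plan says.** SAP 12.1, under joint/bone structural damage, builds the overall change from baseline in two steps. "The joints are divided into 10 segments according to" Table 12-1: five for erosion and five for joint space narrowing (JSN), with left and right sides pooled. Within a segment that reaches its adequacy threshold (5 of 8 or 7 of 12 joints), the change is computed "with missing joints imputed by the within-segment mean change over individual joints". If at least 6 segments are evaluable, the overall change is computed "with missing segments imputed by the mean change over segments"; "if ≤ 5 segments have evaluable change from baseline values", it is missing. No weight or rescaling is stated for the segment step.

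The same section gives the score ranges: "The maximum erosion score is 200 for all 40 hand locations, and 120 for all 12 feet locations", and for JSN "The maximum score is 160 for all 40 hand joints, and 48 for all 12 feet joints". The total runs from 0 to 528. Of the two component scores it says: "The erosion score and joint space narrowing score will be analyzed in similar fashion".

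**The concern.** A segment change has to be a sum over joints. If it were a mean per joint, filling missing joints with the within-segment mean would change nothing. These sums are on different scales, because segments hold 8 or 12 joints and a joint is graded to 4 (JSN), 5 (hand erosion) or 10 (foot erosion). A plain mean of the other segments therefore tends to give a large segment too little and a small one too much.

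Elsewhere the SAP does respect scale. Missing joints take their own segment's mean, and incomplete tender and swollen joint counts are scaled up in proportion to the joints assessed. Only the segment step does not. At stake are the total-score changes of subjects with 6 to 9 evaluable segments.

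The component scores raise a second question. Each has only five segments, so a threshold of six, applied literally, can never be met, even with complete films.

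**Working it through.** **Inputs.** Joint counts and thresholds: SAP Table 12-1. Grades per joint: Protocol 6.4.2, and the hand and foot totals in SAP 12.1 (200/40 = 5, 120/12 = 10, 160/40 = 4, 48/12 = 4).

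**Segment maxima** = joints × top grade:

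| Segment | Erosion | JSN |
|---|---|---|
| PIP | 8 × 5 = 40 | 8 × 4 = 32 |
| DIP | 8 × 5 = 40 | 8 × 4 = 32 |
| MCP + thumb | 12 × 5 = 60 | 12 × 4 = 48 |
| Wrist | 12 × 5 = 60 | 12 × 4 = 48 |
| Foot | 12 × 10 = 120 | 12 × 4 = 48 |
| Sum | 320 | 208 |

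320 + 208 = 528, which reproduces the SAP's total. (Protocol 6.4.2 gives 360 and 168. These also sum to 528 but do not follow from Table 12-1; the point here is unaffected.)

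**Which losses trigger the rule.** Protocol 6.4.2 has each hand and each foot filmed separately.
- One hand film lost: 4 of 8 or 6 of 12 joints remain, below 5 and 7. All eight hand segments go missing, two segments remain, and the overall change is missing. Nothing is imputed.
- One foot film lost: 6 of 12 remain, below 7. Both foot segments go missing, eight remain, and the rule applies.
- PIP or DIP segments go missing on their own only when at least 4 of 8 joints are unscorable on otherwise readable films.

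**Two assumed progression patterns.** The documents give none, so these show a range:
- A: equal points per joint. Each segment's true change is proportional to its joint count (52 + 52 = 104 in all).
- B: change proportional to the maximum (528 in all).

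**SAP rule, both foot segments missing.**
- A: observed 104 − 24 = 80, mean 80/8 = 10, filled 20 against 24. Total 100/104, or −3.8%.
- B: observed 528 − 168 = 360, mean 360/8 = 45, filled 90 against 168. Total 450/528, or −14.8%.

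**SAP rule, all four PIP and DIP segments missing.**
- A: observed 104 − 32 = 72, mean 72/6 = 12, filled 48 against 32. Total 120/104, or +15.4%.
- B: observed 528 − 144 = 384, mean 384/6 = 64, filled 256 against 144. Total 640/528, or +21.2%.

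**Joint-count fill-in within feature** = (sum of observed segment changes of that feature / number of joints in those segments) × joints in the missing segment. Under A it is exact. Under B:
- Both feet: erosion 200/40 × 12 = 60 against 120; JSN 160/40 × 12 = 48 against 48. Error −60/528 = −11.4%.
- All PIP and DIP: erosion 240/36 × 16 = 106.7 against 80; JSN 144/36 × 16 = 64 against 64. Error +26.7/528 = +5.1%.
- MCP + thumb erosions alone (wrist erosions the same): 260/40 × 12 = 78 against 60, or +18/528 = +3.4%. The SAP rule fills (528 − 60)/9 = 52, or −8/528 = −1.5%.

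**Fill-in scaled to segment maxima, feet missing.** Under B it is exact. Under A, erosion is 40/200 × 120 = 24 against 12, and JSN 40/160 × 48 = 12 against 12. Error +12/104 = +11.5%.

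**The case against.** The strongest objection is that the size rests on an assumption the documents do not supply. That stands. For a lost foot film the error runs from 3.8% to 14.8%, and quoting only the upper end would mislead. A reader might infer that the direction is known in advance. It is the same under both patterns above, but it would reverse if a subject's foot segments changed on average less than the hand segments.

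A reader might also infer that any unreadable film biases the total. It does not: a lost hand film makes the overall change missing, and the finger-segment case needs many unscorable joints on readable films. How often that happens is not stated.

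Scaling to segment maxima looks like the obvious repair, but it overshoots by 11.5% for missing feet under equal points per joint. That too stands, and is why it is not proposed as the main rule.

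On the component scores, a reader might conclude that the SAP sets every erosion and JSN change to missing. The text does not go that far. The threshold is written for the overall change, and the sentence on similar analysis may cover only the summaries. What remains is that no segment rule is then given for them.

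Finally, the consequence is limited. Radiographic change is not among the listed primary or secondary objectives, SAP 12.4 plans summaries without formal hypotheses, and Protocol 9.5.1 rules out treatment comparisons for secondary and exploratory variables.

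Nothing else in the SAP removes the problem. Averaging the two readers' scores covers only joints left unscored in a consensus read. The X-ray completers are selected by visits with X-ray measures, not by complete segments.

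**Conclusion.** The point holds in limited form. As written, the rule gives missing foot segments too little and missing PIP and DIP segments too much under both progression patterns examined. For an affected subject the total change is 3.8% to 14.8% too low after loss of a foot film, and 15.4% to 21.2% too high with all PIP and DIP segments missing.

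This assumes that the mean over segments is a plain mean of all observed segment sums. That is the natural reading, though the SAP does not use the word unweighted. If the mean were taken over erosion segments only, a missing foot erosion segment would still receive 50 of 120 (41.7%) under pattern B.

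The effect on group means cannot be computed, because the number of subjects with 6 to 9 evaluable segments is not given. Nothing in the documents shows that it differs by dose. The component scores lack a stated rule, which calls for clarification; a bias in those scores has not been shown.

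**What to change.** 1. Replace the segment fill-in with: mean change per joint over the observed segments of the same feature (erosion or JSN), times the number of joints in the missing segment. With at most 4 of 10 segments missing, each feature keeps at least one observed segment, so the value always exists. For missing foot and PIP/DIP segments this is closer than the present rule under both patterns (feet: 0% to −11.4%; PIP and DIP: 0% to +5.1%). Its drawback is a larger error for missing MCP + thumb or wrist erosions if change is proportional to maximum (+3.4% against −1.5%).
2. Show scaling to segment maxima as a sensitivity analysis.
3. Report, by treatment group and time point, how many subjects have imputed segments and which ones.
4. State that the threshold of at least 6 segments applies to the 10-segment total only, and set a separate minimum for the 5-segment erosion and JSN scores, for example 3 of 5.

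The cost is one formula, two sentences and one count table. The joint counts are already in Table 12-1. The segment maxima for the sensitivity analysis are not listed there and would have to be added. No new data are needed.
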